DigiVis: validation of self-testing visual acuity web-based app to aid ophthalmic telephone consultations during Covid19 lockdown and subsequent social distancing crisis.

Clinical Study Protocol

Protocol Number: DigiVis v0.1

NCT: **IRAS ID 196573**

Document date: **15th July 2020**

Study Title: DigiVis: validation of self-testing visual acuity web-based app to aid ophthalmic telephone consultations during Covid19 lockdown and subsequent social distancing crisis.

Investigational Product: Web-based Visual Acuity software

Protocol Version: Version 0.1

Chief investigator: Miss [name] MBBS MD MA FRCOphth
Consultant Paediatric Ophthalmologist, Addenbrooke's Hospital

Investigator's address: [name], Ophthalmology Department
[name]
Cambridge
[name]

Study Location: Addenbrooke's Hospital, Cambridge (CUHFT)

[contact]

Study Sponsor: Cambridge University Hospitals NHS Foundation Trust

1 Study Synopsis

Title of clinical trial	DigiVis: self-testing vision app for telephone consultations
Sponsor name	Cambridge University Hospitals NHS Trust
Medical condition under investigation	Visual Acuity (VA) assessment
Purpose of clinical trial	To validate VA self-assessment using DigiVis software by comparison to current chart-based tests
Primary objective	Comparison of VA assessment with DigiVis software to clinic-based VA assessment.
Secondary objective (s)	Calculation of test-retest variability. Assessment of usability and preference.
Study Design	Prospective quantifiable comparison study
Study Endpoints	Completed testing on a sufficient number of individuals to give good statistical power.
Sample Size	Approximately 250 patients in total
Summary of eligibility criteria	Patients aged between 5 and 85 due to attend scheduled clinic appointment with vision $+0.8\log\text{MAR}$ (6/38) or better in their left eye. Patients with access to two appropriate digital devices. Ability to understand English and log on to the website.
Active comparator product(s)	Clinic VA charts: LogMAR visual acuity chart, SLT childrens' vision chart.
Route(s) of administration	Visual test
Maximum duration of treatment	2 clinical interventions of 5 minutes each at home
Procedures: Screening & enrolment	Eligible patients will be identified from electronic patient record prior to a scheduled clinical appointment. Telephone enrolment will be undertaken.
Comparators	VA test at the scheduled clinic appointment. Two DigiVis self-test VA measurements. Patient preference.
Intervention period	Two 10 minute phone calls explaining study and the test Two 5 minute self-tests of VA on the website 10 minutes conversation to sign the consent form in clinic and get usability feedback
End of Study	End of scheduled clinic appointment
Procedures for safety monitoring during trial	n/a
Criteria for withdrawal of patients on safety grounds	n/a
Regulatory submissions on safety grounds	Software marked as CE Class I Medical Device

2 Introduction

2.1 Background

Eye problems like macular degeneration and amblyopia (lazy eye) require regular monitoring to prevent permanent visual impairment. Over 2000 patients a month are seen in CUH eye clinics; concern about Covid-19 infection has led to over 80% of consultations being conducted by telephone with few clinical clues to inform decision making. Patients will face long delays even when routine clinics restart: there is no doubt that some will suffer preventable visual loss.

DigiVis is a web-based vision testing app enabling self-testing of vision at home. Early testing and patient feedback is positive: 80% of children prefer DigiVis to regular testing. We wish to test how accurately the app works for home use, by asking older children and adults to self-test their vision prior to their planned face to face clinic appointment. Once tested, DigiVis will be available free of charge to patients, not only during the Covid-19 crisis, but also to support telephonic consultations in the future.

Visual acuity (VA) is a fundamental measure of vision required for all ophthalmic assessments. It is measured by health professionals using vision charts. DigiVis is a new app which enables self-testing of VA using two wirelessly connected digital devices. By matching letters on a handheld device to those displayed on the second device a distance away, threshold VA can be measured using a staircase algorithm. The distance and scaling of the test is vital to its accuracy and a concept (patent filed by Cambridge Enterprise) in DigiVis enables this without the need for manual distance measurement or an observer.

Early validation using two tablet computers in 150 clinic patients has given positive results, both in testing accuracy and patient feedback. With the current Covid-19 crisis limiting face to face appointments, there is an urgent need for accurate home VA assessment. The DigiVis app has been re-coded for free website delivery for this purpose.

We wish to formally validate DigiVis home testing following CE (class I) marking so that it can be recommended for clinical use. 250 patients will be invited to self-test their VA twice using DigiVis prior to a planned face to face clinic appointment. The test-retest variability and comparison of DigiVis VA to chart based assessment will be compared.

The DigiVis test can be undertaken at www.digivis.org with a code name of [name].

2.2 Data from other studies

The DigiVis software app has already undergone initial validation and usability studies in clinic patients, which have resulted in software improvement including a reduction of test time.

A similar study design has been used to assess Peek vision, a smartphone based VA testing app. (1) The difference between DigiVis and Peek app is the automated distance measurement, no requirement for an observer and use of standardised optotype design in the former.

2.3 Safety data

The software is CE marked Class1 medical devices and is delivered on a web-site accessed from the patients' own digital devices, no safety issues are foreseen.

3 Rationale for Study

Validation of the accuracy of the software package will enable recommendation of its use in conjunction with telephone consultation to inform clinical decision making during and after the lockdown period as social distancing increases the need for virtual consultations.

4 Trial objective and purpose

Primary objective: to compare VA assessment of self-testing on the DigiVis website to formal VA measurement using chart-based tests in clinic.

Secondary objective: to assess the repeatability and usability of the software.

4.1 Statement of design

This is a prospective quantifiable comparison study.

4.2 Study duration

Study duration will be 6 months, aiming to start testing by the 3rd June 2020 and complete testing by 3rd February 2021.

4.3 Study objectives

4.3.1 Primary research question

Is the visual acuity score measured by home self-testing with DigiVis comparable to current chart-based clinic methods?

4.3.2 Secondary research question

What is the test-retest variation (repeatability) of the DigiVis system?

What is the ease of use of the app and what features could be modified to improve usability? Study endpoints

4.3.3 Primary endpoint

Clinical testing will cease once at least 250 individuals have been recruited to enable adequate statistical power using Bland-Altman calculations.

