6.1 Informed consent

Subjects who fulfil the inclusion criteria will undergo the following consent process:

First telephone call:

The researcher will telephone patients prior to their scheduled face to face clinic appointment for an introductory phone call to explain the study and to determine if any exclusion criteria apply.

If interested in the study at this first contact, the individual will be directed to the website and shown how to access the study information and consent form. The researcher will go over both forms with the potential participant. A convenient time for a follow up call at least 30 minutes after the first will be arranged to allow the patients

to consider participation and discuss with friends and family. They will be informed that non-participation will not affect patient care. Access to the website is possible via a password and no personal information is stored in the web-server.

Second telephone call:

If the patient wishes to participate in the study they will be asked to read and electronically consent to undertaking the DigiVis test on the website itself. The researcher will then help them undertake the first VA test and will note down the VA values. The participant will be asked to undertake the test themselves a second time before their scheduled clinic appointment and note down, or take a photo of, their VA score.

Clinic assessment:

At this appointment, as standard practice, chart-based VA will be assessed by a health care professional (who is masked to the result of the DigiVis scores). A researcher will approach the subject during their visits and the formal study consent form will be signed and the usability feed-back documented.

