9.1 Statistical methods to be employed

Bland-Altman statistics similar to those illustrated in the initial validation studies will be used. In addition test-retest variability and quantitative comparison of preference and usability will be analysed. Sample size requirements have been calculated using MedCalc based on the results from the initial validation studies (graph 1&2)

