11.3 Declaration of Helsinki and ICH Good Clinical Practise

The study will be carried out in conformation with the spirit and the letter of the declaration of Helsinki, and in accord with the ICH Good Clinical Practice Guidelines

12 Data handling and record keeping

Data with personal information will be kept for analysis 6-12 months following study and subsequently pseudonymised and kept as a file on an NHS hospital computer for a period of 15 years by [name].

13 Financial and Insurance

This trial has been funded by a combination of Addenbrooke's Charitable Trust and Fight Against Blindness charitable funding. The original coding of DigiVis was enabled by an MRC: Confidence in concepts grant in 2016. The investigators will be working within Cambridge University Hospitals NHS Trust and will be indemnified by the NHS.

The VA app will be available free of charge to patients for the foreseeable future.

14 Publications policy

Publications arising from the trial will be authored by [name]. If acceptable accuracy and reliability of DigiVis self-assessment is demonstrated, it is likely that the app will be recommended for the use by the Royal College of Ophthalmologists.

References

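### The primary endpoint is a recruitment stop, no readable text fixes a limit for judging DigiVis comparable with the chart, and in-clinic repeats can stand in for missing home scores

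*Combined protocol and SAP*

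**What the plan says.** Section 4.3.3, headed as the primary endpoint, reads: "Clinical testing will cease once at least 250 individuals have been recruited to enable adequate statistical power using Bland-Altman calculations". The Study Endpoints row of the synopsis is of the same kind: "Completed testing on a sufficient number of individuals to give good statistical power".

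The primary question in Section 4.3.1 is: "Is the visual acuity score measured by home self-testing with DigiVis comparable to current chart-based clinic methods". Section 14 makes likely endorsement conditional: "If acceptable accuracy and reliability of DigiVis self-assessment is demonstrated". On analysis, Section 9.1 states: "Bland-Altman statistics similar to those illustrated in the initial validation studies will be used". It adds that the sample size came from MedCalc and the earlier validation results. Section 5.3 restricts the analysis to the left eye.

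The Comparators row of the synopsis lists: "VA test at the scheduled clinic appointment. Two DigiVis self-test VA measurements". Section 6.1 describes the first DigiVis test as follows: "The researcher will then help them undertake the first VA test and will note down the VA values". For the second it says: "The participant will be asked to undertake the test themselves a second time before their scheduled clinic appointment". Under Section 9.4, if the second test is forgotten or its score is not brought along, DigiVis is repeated in clinic.

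**The concern.** An endpoint should be a quantity measured on participants that can answer the research question. Both endpoint entries can be met in full whatever DigiVis measures.

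The larger gap is the verdict. Section 4.3.1 asks whether the scores are *comparable* and Section 14 speaks of acceptable accuracy. Sections 2.1 and 3 tie the result to recommending the app for clinical use. Bland-Altman analysis describes how far two methods disagree, but not how much disagreement is tolerable. With no limit set beforehand, that judgement can be made with the results in view.

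Two further openings bear on the same result. The plan does not say which DigiVis score is compared with the chart: the first is taken with a researcher's help, the second without. And an in-clinic repeat is not a home test, so using it in place of a missing score mixes settings in an analysis meant to describe home use. The same mixing affects test-retest variability.

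**Working it through.** **1. The plan's own figure.** 100 adults + 150 children = 250 (Sections 7 and 9.2), which agrees with Section 4.3.3 and the synopsis. The power claimed for 250 cannot be reproduced. The readable text gives no mean difference, SD of differences, maximum allowed difference, alpha or power, and the two graphs cited in Section 9.1 are not visible in this copy. The sample size is therefore unreproducible here, not shown to be wrong.

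**2. What is fixed and what is open.**

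| Element | Status |
|---|---|
| Methods compared | Fixed: DigiVis and clinic chart (Sections 4, 4.3.1) |
| Eye | Fixed: left (5.3) |
| Method | Fixed: Bland-Altman (7, 9.1) |
| Outcome named as primary endpoint | Open: 4.3.3 and the synopsis give a stopping point |
| Which DigiVis score | Open: two are recorded (6.2), neither named as primary |
| Limit for *comparable* | Open: none in readable text |
| In-clinic repeats | Allowed by 9.4; no separate analysis stated |

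**3. Precision of a limit of agreement.** This needs no allowed difference. In units of the SD of the paired differences, the 95% CI half-width is t × √(1/n + 1.96²/(2(n−1))).

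- n = 250: 1.9695 × √(0.004000 + 3.8416/498) = 1.9695 × 0.1082 = **0.213 SD**
- n = 225: 1.9706 × √(0.004444 + 3.8416/448) = 1.9706 × 0.1141 = **0.225 SD**
- n = 200: 1.9720 × √(0.005000 + 3.8416/398) = 1.9720 × 0.1210 = **0.239 SD**

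The last two rows show the main analysis if an assumed 10% or 20% of 250 second tests were in-clinic repeats and were set aside.

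**4. How far the choice of limit could matter (illustration).** Assumed rule: agreement is concluded if the 95% CIs of both limits lie inside ±D. With sample mean m and sample SD s this means |m| + s × (1.96 + 0.213) < D at n = 250. The probability was found by integrating over the normal distribution of m and the chi-square distribution of s², with zero bias.

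| D (SD units) | 2.0 | 2.1 | 2.2 | 2.3 | 2.4 | 2.5 |
|---|---|---|---|---|---|---|
| Chance of concluding agreement | 1.5% | 12% | 42% | 78% | 95% | 99.5% |

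Power reaches 80% at about D = 2.31 SD (2.37 SD at a bias of 0.1 SD, 2.57 SD at 0.3 SD). For assumed SDs of 0.08, 0.10, 0.12 and 0.15 logMAR, 2.31 SD is about 0.185, 0.231, 0.277 and 0.347 logMAR. At SD 0.10, moving the limit from 0.20 to 0.25 logMAR takes the chance from 1.5% to 99.5%.

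**5. Mixing settings (illustration).** Suppose in-clinic repeats have an SD 20% lower than home tests, bias is zero, and the home score sits exactly on the boundary (D = 1.96 SD). The pooled SD is √(0.9 + 0.1 × 0.64) = 0.982 with 10% repeats and √(0.8 + 0.2 × 0.64) = 0.963 with 20%. The chance of wrongly concluding agreement rises from 0.5% to 1.4% and 3.6%.

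**The case against.** The best reply is that much of the endpoint problem is labelling. Both entries use the word to mean when testing ends, and the comparison itself is stated elsewhere. That stands: a reader might infer that the trial has no measured primary comparison, and the documents do not support that.

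It is also fair that Bland-Altman is an estimation method. The mean difference and limits of agreement are valid without a margin, and at 250 pairs each limit has a half-width of 0.213 SD whatever margin is chosen. But Sections 4.3.1 and 14 ask for a verdict and Section 4.3.3 claims power, so the gap affects the conclusion even though it leaves the estimates intact.

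A reader might infer that the second score must be primary. The documents do not settle this. The synopsis calls both measurements self-tests and both are done remotely. The first is recorded by the researcher at the time, while the second is recorded by the participant. In-clinic repeats may also be few, since Section 5.6 withdraws anyone unable to test twice.

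Finally, Section 9.5 might be read as contradicting Section 4.3.3 or as a serious source of false conclusions. A minimum of 250 permits more, and the extension is tied to power, not to a failure to show agreement. It is a wording matter.

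**Conclusion.** The concern holds in a limited form. The text alone establishes three things: the stated endpoint cannot answer Section 4.3.1, no readable passage sets a limit for *comparable* or acceptable accuracy, and Section 9.4 lets in-clinic tests replace home scores. The primary DigiVis score also needs naming.

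The size is conditional. The decision rule, SDs, biases and limits in the calculations are assumptions. The swing from 1.5% to 99.5% shows that a limit chosen late could decide the result if the study falls between about 2.0 and 2.5 SD; nothing in the documents shows that it will. The effect of mixing settings depends on an assumed lower SD in clinic. It would be too strong to say that 250 is the wrong number, or that the missing graphs are a fault in the plan. Graphs of earlier results could show the planning values, but no readable passage turns those results into an acceptance limit.

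**What to change.** 1. In Section 4.3.3 and the synopsis, define the primary endpoint as the left-eye paired logMAR difference, DigiVis minus chart, summarised by the mean difference and 95% limits of agreement with confidence intervals. Name one DigiVis score as primary before data are viewed and give the reason. The unassisted second home test is closest to Section 4.3.1; the first is assisted but recorded by the researcher. Report the other as secondary.
2. Analyse in-clinic repeats under Section 9.4 separately from home tests, for both agreement and test-retest variability.
3. State and justify the maximum allowed difference before data are viewed, using the MedCalc planning value if there was one. Judge *comparable* by whether the 95% confidence intervals of both limits lie inside it, and restate the power that 250 gives.

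As a minor addition, Section 9.5 should say that any extension is decided on the SD of the differences alone, before the mean difference and limits are viewed.

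The cost is mainly wording and the loss of post-hoc flexibility. A tight limit may bring a less favourable stated power; if so, the sponsor should state that power and report the limits with their intervals. Setting in-clinic repeats aside widens the intervals somewhat, as shown in step 3 of the working.

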4.4 Criteria for Discontinuation

4.4.1 Individual subject

Request of the child or parent to withdraw from study or cease testing.

5 Selection and withdrawal of subjects

5.1 Inclusion Criteria

- Age between 5 and 85 years scheduled to have face to face appointment within two weeks
- Previous recorded visual acuity of +0.8logMAR (6/38) or better in the left eye

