6.2 Personal data

The personal data recorded for the study will be hospital number and date of birth. Study data will include: DigiVis VA score x 2, chart based VA score, usability score and patient comments.

7 Evaluation of Results

Bland Altman statistical methods and calculation of test-retest variability will be calculated after 100 adults and 150 children have been tested.

8 Assessment of Safety

No safety issues are expected during this study because the patients are using their own devices and the clinic element of the study is standard clinical practice.

9 Statistics

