9.4 Procedure to account for missing or spurious data

The first DigiVis score will be taken down over the telephone at the time of the second call. It is possible that the participant may forget to take the DigiVis a second time or forget to bring the VA score. Where this occurs, the DigiVis test will be repeated in clinic.

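### The intervals between the two DigiVis tests and the chart test are neither fixed, listed as data nor used in the analysis, so true change in acuity can enter the agreement limits and the retest figure mixes unlike intervals

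*Combined protocol and SAP*

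**What the plan says.** The only limit on the gap between DigiVis and the chart is the eligibility rule in section 5.1: "Age between 5 and 85 years scheduled to have face to face appointment within two weeks". Section 6.1 places the first DigiVis test in the second telephone call: "The researcher will then help them undertake the first VA test and will note down the VA values". The only interval it sets is between the two calls, "A convenient time for a follow up call at least 30 minutes after the first will be arranged", and that is time to consider consent, not spacing between tests.

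For the retest, section 6.1 says: "The participant will be asked to undertake the test themselves a second time before their scheduled clinic appointment". No earliest or latest time is given. If the second test is forgotten or the score is not brought, section 9.4 adds: "Where this occurs, the DigiVis test will be repeated in clinic". The chart test is done at the appointment.

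Section 6.2 gives the data items: "Study data will include: DigiVis VA score x 2, chart based VA score, usability score and patient comments". The personal data are hospital number and date of birth. No test date, time or setting is listed. Sections 7 and 9.1 plan Bland-Altman statistics and test-retest variability, and neither mentions the interval. The exclusions in section 5.2 do not refer to unstable vision or a recent change of treatment.

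**The concern.** The primary question is whether DigiVis and the clinic chart agree; the secondary question is how repeatable DigiVis is. Both are answered from paired differences, and a paired difference contains measurement error plus whatever has truly changed between the two measurements. If acuity changes over the gap, the change is attributed to the method: variable change widens the limits of agreement, and a net change shifts the mean difference.

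For repeatability the difficulty is one of definition as well as size. A repeat within minutes and a repeat two weeks later answer different questions, and a repeat in clinic also changes the setting. Pooled without a record of which is which, they give a repeatability figure for an unknown interval. That matters because the protocol intends the results to support recommending the app for clinical use.

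**Working it through.** **The plan's own figures.** The sample size is 100 adults + 150 children = 250, which is consistent throughout. Section 9.1 says it was calculated from earlier validation results, but the text gives no SD of differences, mean difference or agreement limit. The expected limits therefore cannot be reproduced, and the SDs below are assumptions.

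**Possible intervals, from sections 5.1, 6.1 and 9.4.**
- First DigiVis test to chart: up to about 14 days.
- Second DigiVis test to chart: from the same visit up to about 14 days.
- First to second DigiVis test: from minutes to about 14 days, the longest arising when the second is done in clinic.

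The plan does not say which DigiVis score enters the agreement analysis, so either of the first two intervals could apply.

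**Effect on the limits of agreement.** If true change is independent of measurement error:

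SD_observed = √(SD_method² + SD_change²); half-width of the 95% limits = 1.96 × SD_observed.

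With an assumed SD_method of 0.10 logMAR, the half-width without change is 1.96 × 0.10 = 0.196.

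| Assumed SD_change | SD_observed | Half-width | Widening |
|---|---|---|---|
| 0.02 | √(0.0100 + 0.0004) = 0.102 | 0.200 | 2% |
| 0.05 | √(0.0100 + 0.0025) = 0.112 | 0.219 | 12% |
| 0.10 | √(0.0100 + 0.0100) = 0.141 | 0.277 | 41% |

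The result depends heavily on both assumptions. Across SD_method 0.05 to 0.15 and SD_change 0.02 to 0.10, the widening runs from about 1% (0.15 with 0.02) to about 124% (0.05 with 0.10).

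**Against sampling error.** The 95% confidence half-width of one limit is 1.96 × SD × √(1/n + 1.96²/(2(n − 1))). At n = 250 this is 0.212 SD, or 0.021 logMAR at SD 0.10. The widening in the table is 0.004, 0.023 and 0.081 logMAR: well below, about equal to, and nearly four times that figure. More participants narrow the interval around the widened limit but do not remove the widening.

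**A net change.** Suppose 10% of eyes worsened by 0.2 logMAR over the gap (an assumption). The mean difference shifts by 0.10 × 0.2 = 0.02 logMAR. The added variance is 0.10 × 0.90 × 0.2² = 0.0036, so the half-width becomes 1.96 × √(0.0100 + 0.0036) = 0.229, which is 17% wider. If the same share improved instead, the shift would have the opposite sign.

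**Test-retest.** If a share q of pairs spans a gap long enough for change with mean zero, the pooled variance is about SD_retest² + q × SD_change². The planned data do not supply q.

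**The case against.** The case for leaving the plan alone is substantial. Two weeks is a short, stated bound on the scheduled gap, and most eyes may be stable over it. A true-change SD of 0.10 is demanding: under normality it means about 32% of eyes truly changing by 0.1 logMAR or more within the gap, and nothing in the documents supports that. At 0.02 the effect is negligible. Section 6.2 is a short summary, not a case report form. The clinic visit should be traceable through the hospital number, and the researcher takes the first score live on the call and could date it.

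Most of this stands. It limits the likely size and means that the gap for the first DigiVis score is probably recoverable. It does not cover the second test. The participant does that test alone and may either write the score down or photograph it. A photograph might carry a time, but a written note need not, and the plan asks for no time in either case. Nor does the plan use the dates that could be recovered.

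A reader might infer two stronger things. One is that, because the first DigiVis test always precedes the chart, drift runs in one direction and biases DigiVis. A fixed order does not fix the direction of change: clinic patients aged 5 to 85 may include eyes that improve and eyes that worsen, and the documents give no case mix. The other is that section 2.1 shows that vision changes over the gap. It says "Eye problems like macular degeneration and amblyopia (lazy eye) require regular monitoring to prevent permanent visual impairment", which explains why monitoring is needed but says nothing about change within two weeks.

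**Conclusion.** The point holds as a weakness in timing and recording. Following the plan as written produces a repeatability figure of unknown interval and setting, and agreement limits that include any true change over as much as about two weeks. The repeatability problem is the firmer of the two, because the time of the home retest is likely to be lost. The effect on agreement is conditional: about 2% to 41% widening at an assumed method SD of 0.10 logMAR, with independent, zero-mean change of SD 0.02 to 0.10. The documents do not allow a choice within that range.

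A reader might also infer that the interval is unlimited, or that the main agreement analysis must be restricted to short gaps. Neither follows. The two-week rule bounds the scheduled gap; a postponed visit is not addressed, but nothing indicates how often one would occur. No figure in the documents shows that any particular cut-off is needed for the main analysis.

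**What to change.** - **Section 6.2:** add the date, time and setting (home or clinic, assisted or unaided) of both DigiVis tests, and the date and time of the chart test.
- **Section 6.1:** hold the second call as close to the appointment as practical. Ask for the second test within a stated short window after the first, for example 24–48 h, and ask the participant to note when it was done. The length of the window is for the sponsor to choose.
- **Sections 7 and 9.1:** state which DigiVis score is compared with the chart. Keep all participants in the main agreement analysis and add a pre-stated sensitivity analysis limited to short DigiVis-to-chart gaps. Report test-retest for home repeats inside the window, and show out-of-window repeats and the section 9.4 in-clinic repeats separately.

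Tighter timing will not remove the difference between an assisted first test and an unaided second one; recording the setting at least makes it visible.

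The cost is a few data fields, slightly tighter call scheduling and fewer pairs in the main test-retest estimate. No extra visit or procedure is needed.
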